11.4 Unexpected Adverse Drug Reaction

An unexpected adverse drug reaction is an adverse reaction, the nature or severity of which is not consistent with the applicable product information.

11.5 Suspected Unexpected Serious Adverse Reactions (SUSAR)

The Sponsor Investigator evaluates any SAE that has been reported regarding seriousness, causality and expectedness. If the event is related to the investigational product and is both serious and unexpected, unblinding will be carried out by the Sponsor Investigator to re-evaluate the event and eventually classify it a SUSAR. In this case, the Sponsor Investigator will give report including full detail about patient and incident to the local ethics committee within 15 days. In case of fatal SUSAR, reporting to local ethics committee will be given within seven days. Swissmedic will be informed about non-fatal SUSAR within 15 days and in case of fatal SUSAR within seven days.

11.6 Assessment of Severity

Severity of possible AE due to the application of IMPs will be classified as follows.

- Mild: numbness and tingling in the fingers and toes, numbness and unusual sensations around the mouth, a metallic taste in the mouth, ringing in the ears, or lightheadedness and dizziness, local skin reactions (redness, urticaria)
- Moderate: mild side effects with the addition of nausea and vomiting, severe dizziness, decreased hearing, tremors, changes in blood pressure and pulse

- Severe: drowsiness confusion, muscle twitching, convulsions, loss of consciousness, cardiac arrhythmias with hemodynamic instability, cardiac arrest

Events classified as severe adverse reactions due to IMPs will be included to the definition of SAE. Any other event, not applicable to the classification will be documented in the electronic anesthesia protocol and the CRF and assessed by the investigator if discontinuation and/or further treatment is required.

11.7 Reporting of Adverse and Serious Adverse Events

Fatal, life-threatening or relevant events according patients` health will be defined as SAE. Safety outcomes will not be defined as SAE as long as the Investigator considered these events to be exceptional. Primary, secondary and safety events will be recorded on single CRF, though not reported as an SAE, unless the Investigator considered these events to be exceptional.

All events not fitting as primary, secondary or safety outcomes will be reported within 24 hours to the Sponsor Investigator of the study and will again be evaluated by the Sponsor Investigator. Unblinding will be performed by the Sponsor Investigator to evaluate a suspected unexpected serious adverse reaction. SAE resulting in death will be reported to the local Ethics Committee within a week.

All suspected new risks and relevant new aspects of known adverse reactions that require safety-related measures, i.e. so called safety signals, must be reported to the Sponsor/Investigator within 24 hours. The Sponsor Investigator must report the safety signals within seven days to the local Ethics Committee (local event via local Investigator) and to Swissmedic due to study category B.

An annual safety report is submitted once a year to the local Ethics Committee via local Investigator and to Swissmedic due to study category B via the Sponsor Investigator. Any amendment or modification in study sequence and resulting in changed safety conditions for participants will be reported.

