5.4 Safety outcomes

Vital parameters (blood pressure, pulse rate, oxygen saturation) will be recorded digitally by the electronic acute care patient data management system (ACPDMS) during the peri- and postoperative phase and according to institutional standards. Incidence of any potential adverse events (AE) requiring treatment attributable to lidocaine (e.g. local skin reactions, nausea, vomiting, dizziness, ear ringing, etc.), serious adverse events (SAE) (cardiac arrhythmia with relevant hemodynamic outcome, cardiac arrest) or adverse

events related to opiates (respiratory adverse events, ileus). Other outcomes of interest, precisely PONV will not be accounted for an AE.

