11.2 Definition and assessment of (serious) adverse events and other safety related events

An AE is any untoward medical occurrence in a patient or a clinical investigation participant administered a pharmaceutical product and which does not necessarily have a causal relationship with the study procedure. An AE can therefore be any unfavourable and unintended sign (including an abnormal laboratory finding), symptom, or disease temporally associated with the use of a medicinal product, whether or not related to the medicinal product.

A **SAE** is classified as any untoward medical occurrence that:

- results in death
- is life-threatening
- requires in-patient hospitalization or prolongation of existing hospitalization
- results in persistent or significant disability/incapacity
- is a congenital anomaly/birth defect

In addition, important medical events that may not be immediately life-threatening or result in death, or require intensive care treatment, but may require intervention to prevent one of the other outcomes listed above should also usually be considered serious.

SAE should be followed until resolution or stabilization. Participants with ongoing SAE at study termination (including safety visit) will be further followed up until recovery or until stabilization of the disease after termination.

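### Section 11.7 contradicts itself on safety outcomes judged exceptional, and its default keeps listed safety outcomes off SAE reporting, in unresolved conflict with section 9.3

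*Combined protocol and SAP*

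**What the plan says.** Section 11.7 opens with a definition: "Fatal, life-threatening or relevant events according patients` health will be defined as SAE". Two sentences on listed outcomes follow, called A and B here.

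- **A:** "Safety outcomes will not be defined as SAE as long as the Investigator considered these events to be exceptional".
- **B:** primary, secondary and safety events go on the CRF, "though not reported as an SAE, unless the Investigator considered these events to be exceptional".

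The word *exceptional* is not defined. The general 24-hour rule comes next and is limited to other events: "All events not fitting as primary, secondary or safety outcomes will be reported within 24 hours to the Sponsor Investigator". Safety signals have a separate rule: "so called safety signals, must be reported to the Sponsor/Investigator within 24 hours".

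Section 5.4 lists the safety outcomes. They include "serious adverse events (SAE) (cardiac arrhythmia with relevant hemodynamic outcome, cardiac arrest" and adverse "events related to opiates (respiratory adverse events, ileus". Section 11.2 defines an SAE by seriousness, without a causality condition; one criterion is that the event "requires in-patient hospitalization or prolongation of existing hospitalization". Section 11.6 adds severe reactions caused by the IMP to the SAE definition.

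Two further sections set a 24-hour limit. Section 9.3 has IMP-related SAEs reported to the Sponsor Investigator. Section 8.5 has the Principal Investigator told of a recognized SAE, in a paragraph about stopping the infusion.

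**The concern.** Site staff who meet a serious listed outcome need one answer to two questions: is it an SAE, and who must hear of it by when? Section 11.7 gives opposite answers in adjacent sentences. Its default also points away from reporting for the cardiac events that the plan itself calls serious.

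Under section 11.5 the Sponsor Investigator's evaluation of seriousness, causality and expectedness starts from an SAE that has been reported. Section 11.3 asks both the Investigator and the Sponsor-Investigator to assess causality, but does not say how an event kept off SAE reporting reaches the second of them. There is no data safety monitoring committee (1.3) and no interim analysis (10.6), so reports of individual events carry more of the safety oversight. At stake is whether a local judgment of *unrelated* and *not exceptional* decides if a serious event is reported as an SAE.

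**Working it through.** No arithmetic applies: the plan gives no SAE rate or event count. The check sets the passages side by side.

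**Step 1. A against B, for a listed safety outcome.**

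| Investigator's judgment | A | B | Result |
|---|---|---|---|
| Exceptional | not an SAE | SAE report allowed | contradiction |
| Not exceptional | silent | no SAE report | B alone exempts |

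**Step 2. Suppose A is a slip.** If *as long as* in A was meant as *unless*, A and B agree for an exceptional event and the contradiction disappears. B's default remains: a listed outcome that is not judged exceptional is not reported as an SAE. The general 24-hour sentence does not rescue it, because it leaves out primary, secondary and safety outcomes.

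**Step 3. Which sections conflict with which sentence.** A concerns SAE status. Where the event is judged exceptional, A collides with the opening sentence of 11.7 and with 5.4, 11.2 and 11.6, which define or label SAEs. B concerns reporting and does not undo SAE status. Its direct conflict is with the reporting duty in 9.3.

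**Step 4. Trace the 24-hour rules for a serious event not judged exceptional.**

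- *Not a listed outcome:* the general sentence of 11.7 sends it to the Sponsor Investigator.
- *Listed and IMP-related* (for example cardiac arrest attributed to the IMP): 9.3 requires a report to the Sponsor Investigator, while B says it is not reported as an SAE. No section says which prevails.
- *Listed and judged not IMP-related* (for example an opiate-related ileus that prolongs the hospital stay, listed in 5.4 and serious under 11.2): 9.3 does not apply, the general sentence of 11.7 excludes it, and B exempts it. Section 8.5 has no relatedness limit, so its notice to the Principal Investigator may apply. But 8.5 is framed around stopping the infusion, which under 9.4 ends no later than four hours after surgery. Whether it covers later events is not stated.

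**Step 5. What remains in place.** B itself keeps the events on the CRF. Section 11.9 requires all AEs and SAEs to be collected, investigated and documented. Section 11.8 provides follow-up of ongoing events. Fatal SAEs and safety signals have their own reporting rules in 11.7, and 6.4 allows unblinding for an SAE.

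**The case against.** The strongest case against the point has four parts.

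1. **A is probably a wording slip.** This is plausible, and correcting it would remove the contradiction. It would not touch B's default exemption, so the point does not rest on A alone.
2. **Section 8.5 already covers any recognized SAE within 24 hours.** Much of this stands. Section 9.3 is also tied to stopping the drug, so that framing alone is no reason to dismiss 8.5. The Principal Investigator and the Sponsor Investigator may be one person: sections 6.4 and 6.5 give unblinding to the former, 11.5 and 11.7 to the latter. Even so, 8.5 does not say whether it applies after the infusion, and B would still keep the event off SAE reporting.
3. **The sponsor's SOP may settle it.** Section 11.9 points to an SOP with more detail on safety reporting. It is not in the documents, so practice may be better than the text. The protocol would still contradict itself.
4. **The consequence is limited.** An event judged unrelated to the IMP cannot be a SUSAR, and the events are still documented. This stands and limits the weight of the point.

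A reader might infer more: that serious unrelated listed outcomes have no 24-hour notice at all, that SUSARs would be missed, or that B strips events of SAE status. The documents do not support these readings. Section 8.5 may give notice, 9.3 still requires a report for IMP-related SAEs, and B concerns reporting only.

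**Conclusion.** Section 11.7 is wrong as written. This is an internal inconsistency, not a design choice, and it should be fixed. Three things hold:

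- A and B contradict each other for a safety outcome judged exceptional.
- B and the restricted 24-hour sentence take listed safety outcomes off SAE reporting by default, in unresolved conflict with 9.3 when the event is an IMP-related SAE.
- For a serious listed outcome judged not IMP-related, neither 9.3 nor the general sentence of 11.7 provides a report to the Sponsor Investigator, and the reach of 8.5 is unclear.

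Confidence is high for the conflict in the wording and lower for what would happen in practice. The latter depends on the unseen SOP, on whether the two investigator titles denote one person, and on how 8.5 is read. The number of affected events cannot be estimated from the documents.

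**What to change.** Replace sentences A and B of section 11.7. Deleting only the *exceptional* conditions would leave two blanket exclusions. The replacement should say that primary, secondary and safety outcomes are recorded on the CRF, and that any of them meeting the protocol's SAE definition is still reported as an SAE, listed or not. Extend the 24-hour sentence of 11.7 to these events.

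Then reconcile 11.7 with 5.4, 8.5, 9.3, 11.2 and 11.6 on two matters: who receives the report (Principal Investigator or Sponsor Investigator), and which SAE definition applies (11.2 or the opening sentence of 11.7). The text on stopping the infusion can stay as it is.

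The cost is about one paragraph in an amendment, with ethics committee and authority approval under 2.10 if it counts as substantial, and slightly more SAE reporting work.

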11.8 Safety follow-up

Regulatory follow-up will take place seven days after surgery (postoperative day seven) or on day of patient`s discharge, whatever comes first (labeled as "POD X" in the study sequence). Follow-up of patients terminating the study (either regulatory or prematurely) with reported ongoing SAE, or any ongoing AEs or vital signs being beyond alert, will be

conducted by the Sponsor Investigator / study nurses. Patients will either be contacted by phone or mail or by consultation of their general practitioner, or in case of hospitalization or out-patient treatment, visited on ward. During follow-up SAE and AE will be evaluated and documented in the CRF. If treatment is necessary, patients will be given an appointment for out-patient treatment or hospitalization.

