4.3 Other objectives of interest

Other objectives of interest are as follows:

- Monitoring of PONV and its distribution between the groups.
- Comparing time to first defecation after completion of surgery in both groups in regard of a beneficial effect in the “lidocaine group”.
- Comparing length of hospitalization of both groups in regard of a beneficial effect in the “lidocaine group”.

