5.3 Other outcomes of interest

- any event of postoperative nausea and vomiting (subdivided by event of no nausea (PONV = 0), event of nausea without vomiting (PONV = 1) and event of nausea with vomiting (PONV = 2)) during first 48 hours after completion of surgery
- time to first defecation (quantified in hours)
- duration of hospitalization (quantified in days)

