POD 1	ABTEILUNG	VAS Monitoring 6am, 2pm, 10pm Studiensite 10am, 2pm	- Erinnerung des Pat. durch Pflege- Studienpersonal - Prim./Sek. Variablen im CRF erfassen - AE, SAE, ADR erfassen
POD 2	ABTEILUNG	VAS Monitoring 6am, 2pm Studiensite 10am, 2pm (Safety follow-up)	- Erinnerung des Pat. durch Pflege- Studienpersonal - Prim./Sek. Variablen im CRF erfassen - AE, SAE, ADR erfassen
POD X	Studien- koordination	Safety follow-up	- telefonisch / ambulant - AE, SAE, ADR erfassen

table 2: study sequence describing process and daily course, POD X will be postoperative day seven or day of patients discharge

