11. SAFETY ANALYSIS

11.1 Drug studies

During the entire duration of the study, all AE, ADR and all SAE, related to the application of IMPs (severity of possible AE related to lidocaine will be discussed in chapter 11.6) are collected, fully investigated and documented in source documents and case report forms (CRF). Study duration encompassed the time from when the participant signs the informed consent until study nurses final visit on second postoperative day at 2pm respectively +/- 30 minutes.

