11.9 Safety SOP

The Sponsor's standard operating procedures (SOP) provide more detail on safety reporting. During the entire duration of the study, all AE and all SAEs are collected, fully investigated and documented in source documents and CRF. Study duration encompassed the time from when the participant signs the informed consent until the last protocol-specific procedure has been completed, including a safety follow-up period.

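### No single end point is set for adverse-event collection, and on one reading the window closes at discharge and so depends on length of stay

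*Combined protocol and SAP*

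**What the plan says.** All references are to the combined protocol and SAP.

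- Section 11.1 runs AE and SAE collection from consent "until study nurses final visit on second postoperative day at 2pm respectively +/- 30 minutes". Sections 6.1 and 9.4 end study observation at the same visit.
- Section 11.9 defines study duration for the same purpose, but runs it "until the last protocol-specific procedure has been completed, including a safety follow-up period".
- Section 11.8 sets the follow-up at postoperative day seven "or on day of patient`s discharge, whatever comes first". Beyond that it plans contact only for patients who finish with an ongoing AE or SAE, or with vital signs out of range. Section 11.2 likewise follows ongoing SAEs until they resolve or stabilise.
- Table 2 in section 8.1 marks the day-2 visit as safety follow-up. It then lists a further safety follow-up row, POD X, by telephone or out-patient visit, at which AEs are recorded. Its caption says "POD X will be postoperative day seven or day of patients discharge", without saying which of the two applies.
- Length of hospitalization is an outcome (sections 5.3 and 9.2). Section 4.3 lists, among other objectives, "Comparing length of hospitalization of both groups in regard of a beneficial effect" in the lidocaine group.

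**The concern.** Two things are at stake.

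The first is that staff cannot tell from the text when to stop recording AEs. An event on day 4 falls outside the study under 11.1. Under 11.9 it may fall inside.

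The second arises only if 11.8 and 11.9 govern. The window for detecting new events then closes at discharge when that comes before day 7. Discharge happens after randomization, and the trial looks for a lidocaine benefit on it. If lidocaine does shorten stay, its arm is watched for less time and may record fewer events for that reason alone, so the safety comparison would be falsely reassuring. The events exposed are the later ones. Ileus is a named safety outcome in section 5.4. Infection is discussed as a possible lidocaine risk in section 3.5, which also notes that most of the data are reassuring. Readmission would meet the hospitalization criterion for an SAE in section 11.2.

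**Working it through.** **Step 1: the end points side by side.** The plan states no figure on this point, so there is none to reproduce.

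| Source | End of AE/SAE collection | Depends on discharge? |
|---|---|---|
| 11.1 | 2pm on day 2 | No |
| 11.9 | Last procedure, including safety follow-up | Through 11.8 |
| 11.8 | Earlier of day 7 and discharge | Yes |
| Table 2 | Day-2 visit labelled safety follow-up, then POD X on day 7 or discharge | Unclear |

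The follow-up period in 11.9 might be read as the day-2 visit, since Table 2 gives that visit the label. That does not reconcile the text, because the POD X row still records AEs after the end set in 11.1. A telephone or out-patient contact also fits poorly with a contact on the day of discharge. The sections differ in scope too: 11.1 attaches a qualifier about relation to the study products, while 11.9 covers all AEs and SAEs.

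**Step 2: what each reading loses.**

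- Under 11.1 the window is the same in both arms, and 7 − 2 = about 5 of the first seven days go uncounted.
- Under 11.8/11.9, events that begin after discharge and before day 7 have no planned detection. Readmission always follows discharge, so it has no planned detection in either arm. For events such as ileus or infection, the share lost depends on length of stay.

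**Step 3: possible size under 11.8/11.9.** The documents give no length of stay and no AE timing, so both are assumed. Let L and P be the stays in days in the lidocaine and placebo arms, both under 7, with the same true event pattern in each arm.

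- Constant daily rate: apparent deficit = 1 − L/P.
- Front-loaded: a share f of seven-day events falls in days 0 to 2 and the rest is uniform over days 2 to 7. Then F(t) = f + (1 − f)(t − 2)/5, and the deficit = 1 − F(L)/F(P).

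| Assumed stay, L v P | Constant rate | f = 0.5 | f = 0.8 |
|---|---|---|---|
| 2.5 v 3 | 1 − 2.5/3 = 17% | 1 − 0.55/0.60 = 8% | 1 − 0.82/0.84 = 2% |
| 3 v 4 | 1 − 3/4 = 25% | 1 − 0.60/0.70 = 14% | 1 − 0.84/0.88 = 5% |
| 2 v 3 | 1 − 2/3 = 33% | 1 − 0.50/0.60 = 17% | 1 − 0.80/0.84 = 5% |

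**Step 4: cross-check on patients with a first event.** Take a seven-day risk p of 10% to 30%, hazard h = −ln(1 − p)/7, and observed risk 1 − exp(−h × stay). At p = 20%, a 3-day stay gives 0.0912 and a 2.5-day stay 0.0766, a ratio of 0.84. Over the whole range of p the ratios are 0.84 (2.5 v 3), 0.76 to 0.77 (3 v 4) and 0.67 to 0.68 (2 v 3), in line with the constant-rate column. A fixed common window gives 1.00.

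**The case against.** The strongest reply is about timing. The infusion stops at most four hours after surgery (sections 8.1, 8.4 and 9.4), and section 3.1 puts the duration of effect at 30 minutes to three hours. The events listed in sections 5.4 and 11.6 are mostly acute. AEs are recorded in theatre, in the PACU and on the ward through day 2, a period largely common to both arms. This stands: a constant daily rate fits the total AE count poorly, and the front-loaded columns are the better guide to it. They are not a guide to late events taken alone.

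A reader might also infer three stronger things that the documents do not support.

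- *That AE counts are not comparable between arms as the plan stands.* This follows only on the 11.8/11.9 reading. Under 11.1 the window is the same for everyone.
- *That the trial hypothesises a shorter stay.* The hypothesis in section 10.2 concerns pain. Stay is one of the other objectives in 4.3. The evidence on stay in section 3.2 comes from bowel surgery; for the bariatric trial cited there, it reports opiate sparing and satisfaction.
- *That nobody is contacted after discharge.* Patients with ongoing AEs or SAEs are followed (11.8 and 11.2). The gap concerns events that start after discharge.

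Finally, section 11.9 refers to sponsor SOPs for more detail on safety reporting. These are not among the documents and may fix an end point. They would not remove the contradiction in the protocol text.

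**Conclusion.** The point holds in a conditional form. The contradiction over when AE/SAE collection ends is plain on the text. A bias in favour of lidocaine is possible if 11.8 and 11.9 govern and lidocaine shortens stay; if either condition fails, this mechanism produces none. Its size cannot be known from the documents. Across the assumed stays, the apparent deficit runs from 2% to 5% when 80% of events are early, from 8% to 17% when half are, and from 17% to 33% at a constant rate. The last range is an upper-end illustration for the total count, not an estimate. If 11.1 governs, the cost is a short window, equal in both arms, that ends on day 2. The primary endpoint is unaffected on any reading. The plan should be corrected, but the finding does not threaten the main result.

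**What to change.** Reconcile Table 2 and sections 11.1, 11.8 and 11.9 to one calendar window for AE and SAE ascertainment, the same for every patient and independent of discharge. Collection through postoperative day 7, with a telephone contact for patients already discharged, would do this. State in the same edit whether all events or only product-related events are collected, and use the safety follow-up label for one contact only. Keep the existing follow-up of ongoing events. This changes data collection, not treatment.

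The cost is wording plus one short call per discharged patient, so at most 140 calls for 140 randomized patients. Table 2 already lists the telephone mode. It does not contain a fixed day-7 contact, because POD X may be the day of discharge, so the call is a small addition that should be named as such.
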